Investigator: Title: Dermatologist

[contact] [contact]

Test Site: China-Norm U@Test laboratory

Address: [name],

Shanghai, China

Study Objective: To evaluate the effect of a facial essence on skin barrier and skin condition after 2-week of use; And study on the repair efficacy of skin barrier and condition after receiving Fractional Ultrapulse CO₂-laser. The whole study will be divided into two dimensions to evaluate the product: the comparison of the effect before and after and the comparison with the control group.

Experimental Design:

Mono-centric, single-blind, parallel random and home use design.

Test Areas:

Whole face

Subjects:

70 female adult subjects will be enrolled and divided into 2 groups in the study, recruited according to inclusion and non-inclusion criteria listed below, and at least 60 subjects should complete the whole study (at least 30 subjects per group).

Group 1: Facial Serum Group

- Group 2: Non-treatment Group

Age: 20-50 years old

Measurements:

Clinical Assessment(N=60):

Skin qualities of skin dryness, erythema, papules, desquamation, chromatosis, edema, escharosis, elasticity, evenness, brightness, radiance, smoothness, pores on cheek, crow's feet wrinkle, epithelial confluence and overall healthy appearance will be evaluated by dermatologist at T0 (baseline), T14d (after pre-treatment), T15d (Timm post-procedure), T16d (1-day after self-recovery), T18d (3-day after self-recovery), T22d (7-day after self-recovery), T25d (10-day after self-recovery and product treatment start), T32d (7-day after product treatment), T39d (14-day after product treatment) for all groups.

Lactic Acid Stinging Test (N=60)

Sensitive level by Lactic acid test at T0 (baseline), T14d (after pre-treatment), T25d (10-day after self-recovery and product treatment start), T39d (14-day after product treatment) for all groups.

Instrument Assessment(N=60):

- **Corneometer:** skin hydration on both cheeks will be measured at T0 (baseline), T14d (after pre-treatment), T15d (Timm post-procedure), T16d (1-

day after self-recovery), T18d (3-day after self-recovery), T22d (7-day after self-recovery), T25d (10-day after self-recovery and product treatment start), T32d (7-day after product treatment), T39d (14-day after product treatment) for all groups.

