6.2. Products Application and Usage Instruction

Mode of application

a. 1-week wash-out stage: T-7d ~ T0 for all groups

A.M.: Standard cleanser + Standard moisturizer + Standard SPF

P.M.: Standard cleanser + Standard moisturizer

b. 2-week pre-treatment stage: T0 ~ T14d

【Group 1-Facial Serum group】

A.M.: Standard cleanser + Test serum + Standard moisturizer + Standard Sunscreen

P.M.: Standard cleanser + Test serum + Standard moisturizer

Group 2-Non-treatment group

A.M.: Standard cleanser + Standard moisturizer + Standard Sunscreen

P.M.: Standard cleanser + Standard moisturizer

The standard sunscreen needs to apply to face every morning 15 minutes before sun exposure and re-apply if necessary. Keep out of eyes. No any other skin care or facial make up products are used.

c. 10 days recovery stage: T15d ~ T24d for all groups

A.M.: Sterile saline solution + EGF

P.M.: Sterile saline solution

d. 2-week post-treatment stage: T25d ~ T39d

【Group 1-Facial Serum group】

A.M.: Standard cleanser + Test serum + Standard moisturizer + Standard Sunscreen

P.M.: Standard cleanser + Test serum + Standard moisturizer

Group 2-Non-treatment group

A.M.: Standard cleanser + Standard moisturizer + Standard Sunscreen

P.M.: Standard cleanser + Standard moisturizer

The standard sunscreen needs to apply to face every morning 15 minutes before sun exposure and re-apply if necessary. Keep out of eyes. No any other skin care or facial make up products are used.

7. Procedure

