7.2. Conducting the Study

Pre-screening visit at T-7d

- a. Within 24 hours before screening visit, subjects will be asked not to use any cosmetic product on test areas.
- b. On the arrival, the subject will be informed about the nature of the study and the treatment procedure and a signed and dated informed consent form will be obtained. At the same time, one Photo release form will be also signed from each subject.
- c. A subject screening number will be automatically allocated (SC0X) by CRF.
- d. Demographic data collection.
- e. Medical examination, subject's interview on his medical history and concomitant medications.
- f. Subjects wash face with usual cleanser, then pat dry with clean tissue paper at center.
- g. Acclimatization to the room condition for 30 minutes (the conditions with a well-controlled room temperature (21 ± 1 °C) and humidity ($45\%\pm5\%$).
- h. Clinical assessment by will be done by dermatologist for screening.
- i. Verification of subject eligibility: inclusion/non-inclusion criteria and on-site clinical grading by Dermatologist.
- j. The weighted wash-out products and daily log will be delivered to each subject.
- k. Adverse Events/Local Intolerance will be checked and recorded.

Evaluation visit on T0: Baseline

- a. Subjects wash face with usual cleanser, then pat dry with clean tissue paper at center.
- b. Acclimatization to the room condition for 30 minutes (the conditions with a well-controlled room temperature (21 ± 1 °C) and humidity ($45\%\pm5\%$).
- c. Verification of inclusion/non-inclusion criteria for final eligibility.
- d. Clinical Assessment will be done by dermatologist for T0.
- e. VISIA 7 will be done by trained technician for T0.
- f. OCT scan will be done by trained technician for T0.
- g. Corneometer will be done by trained technician for T0.
- h. Vapometer will be done by trained technician for T0.
- i. Cutometer will be done by trained technician for T0.
- j. pH meter will be done by trained technician for T0.

- k. LA sting test will be done by trained technician for T0.
- The wash-out (standard) products will be weighted and returned to subjects; as the same time, the weighted
 investigational products and daily log will be delivered to each subject according to the randomization
 table.
- m. Adverse Events/Local Intolerance will be checked and recorded.

T0 to T14d

a. Subjects should apply the provided wash-out products twice a day at home, in the morning and in the evening.

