8.3. Efficacy Verification

8.3.1 Comparison between Time-points

A Shapiro-Wilk test will be used to test for normality of the baseline data (T0) and the change from baseline data (Tn-T0) at post-baseline time points at significance level alpha=0.01. When data passes normality (all normality of the distributions is confirmed for the same parameter), a parametric test will be used to test the null hypothesis that the mean change from baseline is zero. When data fails normality (if one or more normality of the distributions for the same parameter is rejected), a non-parametric test will be used.

Pre-treatment efficacy:

- a) T14d (after pre-treatment), T15d (Timm post-procedure) versus T0 (baseline)
- b) T16d (1-day after self-recovery), T18d (3-day after self-recovery), T22d (7-day after self-recovery), T25d (10-day after self-recovery) versus T15d (Timm post-procedure)

Post-treatment efficacy:

a) T32d (7-day after product treatment), T39d (14-day after product treatment) versus T25d (product treatment start)

The following will be calculated and reported for each evaluation parameter at applicable post-statistical baseline time point(s):

For self-assessment questionnaires, only the data of completing subjects will be analyzed. Questionnaire response options will be in the form of a 5-point semi-structured scale, ranging from one (1) to (5), where the score of one (1) will be the most negative/unfavorable rating and the score of five (5) will be the most positive/favorable rating the product can receive (the scale will also include a mid-point label "neither agree nor disagree"). Responses obtained for each question will be tested for normality using a Shapiro-Wilk test at significance level alpha=0.01, and if the data passes normality testing, mean scores will be used. Responses that are not normally distributed will be assessed using the median response. The percentage of ratings from

4 to 5 ("top XX box %") will be reported.

In the report appendices, raw data and open-ended questionnaire responses will be listed by subject. Data frequency and percentage will be presented for questionnaires and tolerability evaluations. Tolerability tables will also be sent to the Sponsor at the indicated interim data time points; SAQ data will be sent at study completion, for all completing subjects. Medians, means and percentage values will be reported to decimal place (0.0) for all questionnaire data.

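### Section 8.3.1 b counts change from T15d as pre-treatment efficacy, although T15d already follows 14 days of randomised serum use; compared between groups, this change hides or can reverse a serum effect on the laser injury

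*Protocol*

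**What the plan says.** The Protocol describes a "Mono-centric, single-blind, parallel random and home use design". One objective is to study "the repair efficacy of skin barrier and condition after receiving" the fractional laser, judged both before and after and against the control group.

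- **Allocation.** At the T0 visit (section 7.2) the "investigational products and daily log will be delivered to each subject according to the randomization" table, so T0 is the last value before randomised product use.
- **Serum exposure before the laser.** Section 6.2 sets "b. 2-week pre-treatment stage: T0 ~ T14d". Only Group 1 has the serum in that stage; Group 2 uses the standard products alone.
- **Care after the laser.** Section 6.2 then sets "c. 10 days recovery stage: T15d ~ T24d for all groups", with the same regimen in both groups and no serum listed.
- **Comparisons over time.** Section 8.3.1, under pre-treatment efficacy, has two items. Item a is "T14d (after pre-treatment), T15d (Timm post-procedure) versus T0 (baseline". Item b takes T16d, T18d, T22d and T25d, each against the immediate post-laser value, ending with "T25d (10-day after self-recovery) versus T15d (Timm post-procedure".
- **Comparison between groups.** Section 8.3.2 names a t test of Group 1 against Group 2 and lists the attributes. It does not say whether visit values or changes are compared, or from which reference.

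**The concern.** Care is identical from T15d to T24d, so in that window the groups differ by design only through earlier serum use. That use ends before T15d is measured, and any protection or aggravation it causes may already be in the T15d value. Taking T15d as the zero point then removes part of the effect that the label says is being measured.

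At stake is how the repair objective is read. Suppose a reader compares the two groups' changes from T15d, or section 8.3.2 tests them. A serum that limits the initial injury leaves less to recover, and one that aggravates it leaves more. The 0 to 5 symptom scores in section 5.1 push the same way: a score cannot fall below 0, so the largest possible improvement from T15d is the T15d score itself.

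**Working it through.** The Protocol gives no effect size, SD or power figure, so there is nothing of its own to reproduce. From the Protocol: 30 completers per group (Subjects), two-sided 5% (section 8.1), and the references in 8.3.1. Everything else below is assumed.

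**1. Algebra.** Let δ15 and δ25 be the serum-minus-control differences at T15d and T25d, with groups equal at T0. The between-group contrast of change from T15d is δ25 − δ15.

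- Difference constant (δ25 = δ15): contrast 0, so the effect is hidden.
- Difference narrows with the same sign: the contrast has the opposite sign to the true effect.
- Difference widens: right sign, but smaller than δ25 by δ15.

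The contrast of change from T0 at T25d is δ25 itself.

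**2. Size.** Assume SD 1 at each visit and correlation ρ between visits. The SD of a change is √(2(1 − ρ)), the standardised difference is d = |δ25 − δ15| / SD of change, and the noncentrality is d / √(2/30) on 58 degrees of freedom.

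*Scenario 1: serum worsens T15d by 0.5 SD, groups equal at T25d. The contrast is 0.5 SD in favour of serum.*

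| ρ | SD of change | d | Significant for serum |
|---|---|---|---|
| 0.3 | 1.18 | 0.42 | 36% |
| 0.5 | 1.00 | 0.50 | 48% |
| 0.7 | 0.77 | 0.65 | 69% |

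A simulation of 20,000 trials gave 36.0%, 48.0% and 68.9%. With T0 as reference at T25d, a significant result for serum occurred in 2.4% to 2.7%.

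*Scenario 2: serum better by 0.5 SD at T15d and by 0.25 SD at T25d. The contrast is 0.5 − 0.25 = 0.25 SD against serum.*

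| ρ | d | Noncentrality | Estimate points the wrong way | Significantly wrong |
|---|---|---|---|---|
| 0.3 | 0.21 | 0.82 | 79% | 12% |
| 0.5 | 0.25 | 0.97 | 83% | 16% |
| 0.7 | 0.32 | 1.25 | 89% | 23% |

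The fourth column is Φ(noncentrality); the fifth is from the noncentral t distribution.

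**3. A second model.** Assume the laser raises a score by 3 points in control, the serum prevents 25% of that (rise 2.25), and both groups heal 70% by T25d.

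- Recovery from T15d: control 0.7 × 3 = 2.10; serum 0.7 × 2.25 = 1.575. Serum looks 0.525 worse.
- Residual against T0: control 0.3 × 3 = 0.90; serum 0.3 × 2.25 = 0.675. Serum is 0.225 better.
- Break-even: the serum group must heal 0.7 / 0.75 = 93% to show equal recovery.
- If both groups instead heal by the same 2.10 points, the T15d contrast is 0 and the effect is hidden, not reversed.

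**4. Scope.** The point concerns the clinical, instrumental and imaging measures, taken at T0 and at every visit from T15d to T25d. The lactic acid test is not done at T15d, and the post-procedure tolerance questionnaire is not given at T0.

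**The case against.** The strongest reply is that section 8.3.1 is a within-group analysis. It tests whether a mean change is zero, and for one group the change from T15d is an ordinary account of healing. It contains no serum-control contrast and so cannot by itself have a wrong sign. Section 8.3.2 never says that change from T15d is tested between groups; its attribute list fits visit values at least as well, and the choice may lie in an analysis plan not shown. If visit values are compared, none of the percentages applies. **This stands**, and it makes the harm conditional. What remains is that 8.3.1 b carries an efficacy label, and that T15d is the only reference it gives for the recovery visits.

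Second, item a tests T15d against T0, so an effect on the injury is not lost. In scenario 1 a between-group comparison of that change has the same d and would show the harm in the same 36/48/69% of trials. **This also stands**, but the two results would then conflict, and the Protocol does not say which one answers the repair question.

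Third, speed of healing from the injured state is a legitimate question under the objective. **Agreed**, provided the T15d versus T0 result is shown beside it.

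The clause in 8.3.1 that permits a more appropriate analysis names none, so it does not settle the matter.

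**Conclusion.** The concern holds in conditional form. The Protocol labels as pre-treatment efficacy a change whose reference is measured after randomised treatment, and it leaves open whether that change enters the group comparison. If it does, an effect on the initial injury is hidden when the group difference stays constant and reversed when it narrows.

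A reader might infer that the repair objective will come out with the wrong sign, or that a protective serum must always show less recovery. The documents support neither. No between-group test of change from T15d is specified, and a serum that speeds healing beyond the break-even would still show more recovery. The 79/83/89% also counts only the direction of the estimate; significant wrong-way results are about 12/16/23%.

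All percentages rest on the assumed effects, SD of 1 and correlations of 0.3 to 0.7. They show that the problem could matter at 30 per group; they do not predict this trial. The change should be made because it costs almost nothing and removes a post-randomisation reference.

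**What to change.** - **Section 8.3.1 b:** keep change from T15d at T16d, T18d, T22d and T25d, but call it a within-group description of healing and not evidence of pre-treatment efficacy.
- **Section 8.3.2:** state that for T15d to T25d the primary comparison of Group 1 with Group 2 is of visit values adjusted for the T0 value, for example by ANCOVA. Any between-group comparison of change from T15d is supportive only and is shown beside the T15d versus T0 result. Measures without a T0 value, such as the tolerance questionnaire, are compared on visit values unadjusted.

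Cost: a few sentences in two sections. The T0 values are already scheduled, so there is no new visit, measurement or subject.

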8.1. Statistical considerations

All statistical tests will be two-sided and at the 5% level of significance.

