8.3.2 Comparison between Treatments

Paired T test for the same sample size or the independent T test for the different sample size will be used to identify the difference efficacy between treatments if the data fit normal distribution.

- Group 1-Facial Serum group
- **Group 2-**Non-treatment control group

Evaluation	Attributes	Comparison
Clinical Assessment	•Skin symptoms scoring post-procedure: - Dryness - Erythema - Papules - Desquamation - Chromatosis - Edema - Escharosis •Skin qualities: - Skin elasticity - Skin evenness - Skin brightness - Skin smoothness - Skin radiance - Appearance of pores on cheek - Crow's feet wrinkle - Epithelial cell confluence - Over healthy appearance	Group 1 versus Group 2
Instrumental Assessment	Skin hydration by Corneometer Transepidermal water loss (TEWL) by Vapometer Skin elasticity by Cutometer Skin pH by Skin-pH-Meter	
Imaging Analysis	Attributes output from VISIA 7 Attributes output from OCT (The thickness of epidermis)	
LA stinging Test	•Skin symptoms scoring: - Stinging - Itching - Burning	
Tolerance Feedback	•Skin symptoms scoring: - Area - Severity - Start time - During time	

9. Further Study Documentation

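### Section 8.3.1 lists under pre-treatment efficacy within-group contrasts (T16d to T25d versus T15d, and T15d versus T0) that reflect the laser injury and its healing and cannot show a serum effect

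*Protocol*

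**What the plan says.** The Study Objective includes a "study on the repair efficacy of skin barrier and condition after receiving Fractional Ultrapulse" CO2 laser treatment, and says that the whole study is "divided into two dimensions to evaluate the product: the comparison of the effect before and after and the comparison with the control group".

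Section 8.3 (Efficacy Verification) has two parts. Section 8.3.1 compares time points: if the data pass a normality check, "a parametric test will be used to test the null hypothesis that the mean change from baseline is zero", and otherwise a non-parametric test is used. Its pre-treatment efficacy list has two items:

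- a) T14d and T15d versus T0;
- b) T16d, T18d, T22d and T25d versus T15d, the last being "T25d (10-day after self-recovery) versus T15d (Timm post-procedure").

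Section 8.3.2 compares Group 1 (serum) with Group 2 (no treatment): a t test "will be used to identify the difference efficacy between treatments if the data fit normal distribution". Its table covers the clinical, instrumental, imaging, stinging and tolerance attributes. It names no time points and no change variable.

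Section 7.2 places the laser at the T15d visit, followed by that visit's clinical, imaging and instrumental readings. Section 6.2 c sets the care from T15d to T24d for all groups: "A.M.: Sterile saline solution + EGF", and saline alone in the evening. In section 6.2 the serum appears only in Group 1, from T0 to T14d and again from T25d.

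**The concern.** The label on item b) says that a significant result bears on the efficacy of serum pre-treatment. The reference for the change, however, is freshly lasered skin. Skin that heals at all moves away from a zero-change null, with or without serum beforehand. Healing alone breaks the attribution, and the EGF and saline care given to both groups is a second cause.

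Item a) has the mirror-image fault at T15d. The change from T0 contains the injury that the laser has just made, so a departure from zero is again expected whatever the serum does. A benefit could show only as a smaller injury than in untreated skin, which one group alone cannot reveal.

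Recovery after the laser is a stated aim, and before-after change stands beside the control comparison as a way to evaluate the product. The protocol does not rank one above the other. A positive within-group result could therefore be cited for the serum even if the groups did not differ.

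**Working it through.** **Inputs from the protocol.** Section 8.1: "All statistical tests will be two-sided and at the 5% level of significance". The Subjects section: "at least 60 subjects should complete the whole study (at least 30 subjects per group"), so n = 30 per group. The protocol gives no SD, expected change or power, so there is no figure of its own to reproduce.

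**Assumption.** Let d be the mean change divided by the SD of the change, the same in both groups, with zero serum effect and normal changes. For item b), d stands for healing plus common care. For T15d versus T0, it stands for the laser injury plus the standard products. These figures do not isolate EGF.

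**What each contrast contains.**

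- Item b), Group 1: healing + common care + serum carry-over.
- Item b), Group 2: healing + common care.
- Group 1 minus Group 2: serum carry-over only.

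**Within-group test.** Paired t test with 29 degrees of freedom and non-centrality d × √30. At d = 0.5 this is 0.5 × 5.477 = 2.74, which gives a rejection probability p of 0.754. The chance that Group 1 is significant and Group 2 is not is p(1 − p): 0.754 × 0.246 = 0.186.

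| d (assumed) | P(significant), t test | P(significant), signed-rank (simulated) | Group 1 significant, Group 2 not |
|---|---|---|---|
| 0.2 | 18.5% | 17.8% | 15.1% |
| 0.3 | 35.6% | 33.9% | 22.9% |
| 0.5 | 75.4% | 73.3% | 18.6% |
| 0.8 | 98.9% | 98.5% | 1.1% |
| 1.0 | 99.96% | 99.9% | 0.04% |

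A separate simulation of 20,000 trials at d = 0.5 gave significance in 75.1% for one group and 75.7% for the other. The test behaves the same way in subjects who never use the serum.

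**Between-group test.** The independent t test on the same simulated data rejected in 4.8% to 5.2% of trials at d = 0.5, 1.0 and 1.5. The common shift cancels, so healing and EGF do not bias it.

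**Which reference for the between-group comparison.** Let D15 and D25 be the serum benefit (Group 1 minus Group 2) at T15d and T25d. The group difference in change from T15d is D25 − D15.

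- If serum lessens the immediate laser reaction and the benefit persists unchanged, D25 = D15 and the result is zero.
- If serum lessens the reaction and both groups heal to the same level by T25d, D25 = 0 and the result is −D15, which looks like harm.

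T15d follows 14 days of serum, so this can happen. T0 precedes any serum and does not have the problem.

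**The case against.** The strongest reply is that the control comparison is already planned. Section 8.3.2 sets Group 1 against Group 2 on every attribute family, including the symptoms scored after the procedure. Section 8.3.1 is titled as a comparison of time points, and pre-treatment is also the name of a study phase. This stands, and it limits the point: the protocol does not lack a controlled comparison. It does not remove the point, because 8.3.1 sits under efficacy verification and the item's heading says efficacy.

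A reader might infer that the protocol will declare efficacy from item b), or from Group 1 being significant while Group 2 is not. The document does not support that. It sets no success criterion on item b) and no rule on such a pattern. The last column of the table therefore describes a possible misreading, and it falls to about 1% or less at shifts of 0.8 SD and above.

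Three narrower objections also have weight:

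- Section 8.3.1 does not say in which groups item b) is run. Reading it as within-group follows from 8.3.2 being the between-group section.
- The null is worded as change from baseline, with T0 as baseline, while item b) refers to T15d. Zero change from T15d is the natural reading, but it is not literally stated.
- A significant two-sided change could be a worsening, which would not favour the serum. That is true, and it shows that the test follows the course of the laser reaction rather than the product.

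Section 8.3.1 ends by allowing a more appropriate analysis to be recorded later. That permits a correction but does not specify one.

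**Conclusion.** The point holds as one of labelling and interpretation. Item b), and the T15d versus T0 part of item a), cannot show an effect of serum pre-treatment, yet both are listed as tests of it. That conclusion rests on the design alone: the reference or end point is the immediate post-laser reading, and care is common to both groups during recovery. The size is illustrative. With 30 subjects and no serum effect, a within-group test is significant in 19% of trials at an assumed common shift of 0.2 SD, 75% at 0.5 SD and over 99.9% at 1.0 SD.

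It would go too far to say that the trial cannot evaluate recovery, or that EGF biases the group comparison. EGF and healing are common to both arms, and the between-group test stays at about 5%. The change is worth making before the data are read, because a sound comparison exists and the protocol currently places an uninformative one beside it.

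**What to change.** 1. Take item b), and T15d versus T0 from item a), out of the efficacy tests in 8.3.1. Report them descriptively for each group, with estimates and confidence intervals, as the course of the laser reaction and of recovery under common saline and EGF care.
2. State in 8.3.2 that any claim that serum pre-treatment aids recovery rests on Group 1 versus Group 2 at T15d, T16d, T18d, T22d and T25d. Use an independent-groups analysis whatever the group sizes, adjusted for the T0 value or as change from T0.
3. Show the between-group difference in change from T15d as supportive only, since T15d may already carry a serum effect.

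This costs a few lines of wording. Section 4 already schedules the clinical, instrumental and imaging readings in both groups at these visits, so no visits, measurements or subjects are added. The sponsor gives up something real: within-group improvement alone could no longer be cited as product efficacy. The controlled comparison is also more demanding. With 30 per group, an unadjusted test has approximate power of 21%, 49%, 81% and 87% for true group differences of 0.3, 0.5, 0.73 and 0.8 SD of the analysed variable.
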